10.5 UPENN IRB Notification by Investigator-Sponsor

The University of Pennsylvania IRB (Penn IRB) requires expedited reporting of those events related to study participation that are unforeseen and indicate that participants or others are at increased risk of harm. The Penn IRB will not acknowledge safety reports or bulk adverse event submissions that do not meet the criteria outlined below. The Penn IRB requires researchers to submit reports of the following problems within 10 working days from the time the investigator becomes aware of the event:

• Any adverse event (regardless of whether the event is serious or non-serious, on-site or off-site) that occurs any time during or after the research study, which in the opinion of the principal investigator is:

Unexpected (An event is "unexpected" when its specificity and severity are not accurately reflected in the protocol-related documents, such as the IRB-approved research protocol, any applicable investigator brochure, and the current IRB-approved informed consent document and other relevant sources of information, such as product labeling and package inserts.)

AND

Related to the research procedures (An event is "related to the research procedures" if in the opinion of the principal investigator or sponsor, the event was more likely than not to be caused by the research procedures.)

Deaths occurring for patients on-study and within 30 days of study drug administration that are considered unforeseen and indicates participants or others are at increased risk of harm (i.e. unexpected and probably/definitely related), must be reported to the IRB within 24 hours of notification.

Copies of each report and documentation of IRB notification and receipt will be kept in the Clinical Investigator's study file.

For clinical drug trials, the following events are also reportable to the Penn IRB:

- Any adverse experience that, even without detailed analysis, represents a serious unexpected adverse event that is rare in the absence of drug exposure (such as agranulocytosis, hepatic necrosis, Stevens-Johnson syndrome).
- Any adverse event that would cause the sponsor to modify the investigators brochure, protocol or informed consent form, or would prompt other action by the IRB to assure protection of human subjects.
- Information that indicates a change to the risks or potential benefits of the research, in terms of severity or frequency. For example:
 - An interim analysis indicates that participants have a lower rate of response to treatment than initially expected.
 - Safety monitoring indicates that a particular side effect is more severe, or more frequent than initially expected.
 - A paper is published from another study that shows that an arm of your research study is of no therapeutic value.
- Change in FDA safety labeling or withdrawal from marketing of a drug, device, or biologic used in a research protocol.
- Breach of confidentiality
- Change to the protocol taken without prior IRB review to eliminate apparent immediate hazard to a research participant.
- Incarceration of a participant when the research was not previously approved under Subpart C and the investigator believes it is in the best interest of the subject to remain on the study.
- Complaint of a participant when the complaint indicates unexpected risks or the complaint cannot be resolved by the research team.
- Protocol violation (meaning an accidental or unintentional deviation from the IRB approved protocol) that in the opinion of the investigator placed one or more participants at increased risk, or affects the rights or welfare of subjects.

The IRB will accept other reports when the investigator is unsure whether the event should be reported, and the IRB will review such reports to determine whether the event meets the threshold for an unanticipated event presenting risk to the participant.

Office of Regulatory Affairs, Institutional Review Board [name] [contact] [contact]

10.5.1 Reporting Process to IRB at Penn.

Unanticipated problems posing risks to subjects or others as noted above will be reported to the Penn IRB using the form: "Unanticipated Problems Posing Risks to Subjects or Others Including Reportable Adverse Events" or as a written report of the event (including a description of the event with information regarding its fulfillment of the above criteria, follow-up/resolution and need for revision to consent form and/or other study documentation).

Copies of each report and documentation of IRB notification and receipt will be kept in the Clinical Investigator's study file.

10.5.2 FDA Notification by Investigator-Sponsor.

This study is IND exempt and reporting to the FDA is voluntary using a MedWatch 3500 or via the FDA's website for voluntary reporting.

10.6 Medical Monitoring

It is the responsibility of the Principal Investigator to oversee the safety of the study at the site. This safety monitoring will include careful assessment and appropriate reporting of adverse events, as noted above, as well as the construction and implementation of a site data and safety monitoring plan. Medical monitoring by an independent clinician, [name], Department of Medicine, Division of Hematology-Oncology will review comprehensive safety data at least biannually. This will include a real-time review of unexpected and related SAEs and any deaths that are unexpected or occur from the start until 90 days from the last study treatment. The Medical Monitor will also be consulted in the case of exception requests or the evaluation of deviations that may compromise subject safety or disrupt the design of the study. This information will be communicated to the Medical Monitor via email and filed in the Regulatory Binder/Subject Chart appropriately. As applicable, correspondence will be included in IRB/ACC DSMC submission of these events. [name] will be reached at [contact] . Ophthalmic safety concerns that develop during the study will be forwarded to Array for review, as well as the independent medical monitor.

10.7 Study Monitoring Plan

This study will be monitored in accordance with the Cancer Center's Clinical Trials Scientific Review and Monitoring Committee (CTSRMC) Plan, approved by NCI during the Core Grant's most recent review. This plan requires that the investigator submit a study-specific plan outlining how data will be reviewed In addition, the CTSRMC plan calls for an internal audit by the Cancer Center's Data Safety Committee twice yearly. The investigator will allocate adequate time for such monitoring activities. The Investigator will also ensure that the monitor or other compliance or quality assurance reviewer is given access to all the above noted study-related documents and study related facilities (e.g. pharmacy, diagnostic laboratory, etc.), and has adequate space to conduct the monitoring visit.

10.8 Auditing and Inspecting

The investigator will permit study-related monitoring, audits, and inspections by the IRB, government regulatory bodies, and University compliance and quality assurance groups of all study related documents (e.g. source documents, regulatory documents, data collection

instruments, study data etc.). The investigator will ensure the capability for inspections of applicable study-related facilities (e.g. pharmacy, diagnostic laboratory, etc.).

Participation as an investigator in this study implies acceptance of potential inspection by government regulatory authorities and applicable University compliance and quality assurance offices.

If an audit of this or any other study is requested by any regulatory authority, the Investigator will inform Array of the request. The study site will permit access to all necessary records.

11.0 STATISTICAL CONSIDERATIONS

11.1 Design

This is a single arm phase II study of Binimetinib and Hydroxychloroquine for patients with advanced KRAS mutant NSCLC. This study will be conducted in two stages using Simon's Optimal Design (Controlled Clinical Trials 10:1-10, 1989). A number of innovative correlative studies are planned.

11.2 Objectives

The primary objectives are to determine:

- objective response rate (ORR)
- safety & tolerability

The secondary objectives are to determine:

- progression-free survival (PFS) and overall survival (OS)
- changes in ctDNA KRAS allelic frequency (blood)

The correlative objectives are to determine:

- association between objective response and pre-treatment tumor expression of PPT1, LC3, ALDH1A1 and HLTF biomarkers
- differences in pre-treatment and Week 6 tumor expression of PPT1, LC3, ALDH1A1 and HLTF biomarkers
- changes autophagic vesicles/cell in serial tumor tissue samples
- evaluate pharmacokinetics and pharmacodynamics of HCQ, to determine whether changes in blood-based autophagy biomarkers reflect tissue-based changes in autophagy (See Section 18)

11.3 Endpoints

- Objective Response will be scored using RECIST. The objective response rate is defined as the percentage of patients who achieve a complete or partial response. Following an intent-to-treat analysis plan, all patients who receive at least one dose of the combination regimen will be included in the analysis of response.
- Duration of response: from time of first catageroization as a PR or CR to the time of progressive disease.
- Safety: NCI Common toxicity criteria (CTCAE v5.0) will be employed to grade toxicities.

- Progression-free survival will be defined as days from start of treatment to first documented disease progression, death due to any cause or last patient contact. Patients who are alive and have not progressed at the time of statistical analysis will be censored on the most recent date that progression-free status is documented (i.e., imaging date). For patients treated beyond progression (in the setting of an isolated lesion) with consent of study chair, PFS will be time to first progression but time to second progression will be recorded separately.
- Overall survival will be defined as days from start of treatment to death due to any cause or last patient contact. Patients who are alive at the time of statistical analysis will be censored for survival.
- Biomarkers: PPT1, LC3, ALDH1A1 and HLTF will be measured in pre-treatment tissue and at Week 6.
- Median number of autophagic vesicles/cell in tumor tissue
- HCQ PK-PD (See Section 11.5)

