1.3 Correlative Objectives

- To evaluate the correlation between response to HCQ + B and pre-treatment tumor staining for PPT1, LC3, ALDH1A1, and HLTF by immunohistochemistry.
- To monitor changes on a repeat biopsy after 3 weeks of treatment with HCQ + B in PPT1, LC3, ALDH1A1, and HLTF by immunohistochemistry, as well as in gene signatures.
- To measure the change in median number of autophagic vesicles/cell (mAV/cell) in serially collected tumor tissue with HCQ + B.
- To determine if blood based candidate biomarkers of autophagy modulation (including IL-8, Interleukin-1 Beta, LIF, DKK3, and FAM3C, and other serum cytokines) reflect autophagy dynamics in tumors of patients treated with HCQ + B.
- To characterize HCQ pharmacokinetics when HCQ is combined with binimetinib
- To monitor changes in allelic fraction of KRAS in circulating tumor DNA (ctDNA) among patients treated with HCQ + B

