7.3 Pharmacodynamic Studies in tumor tissues

7.3.1 Serial Tumor Biopsies and analysis.

Optional serial tumor biopsies are included in the budget for this study. We anticipate that 5 patients will complete at least two serial biopsies (10 total biopsies). Biopsy of easily accesible lesions that do not require radiological guidance will be conducted either by the medical oncologists, surgical oncologist, dermatologists or dermatological surgeons. The procedures involved include: excisional biopsies, excisions of large tumors in the operating room, and core needle biopsies. For core needle biopsies we request 4 cores if possible. The radiologist m ay choose the size of the needle. Lesions that are not easily accesible can be biopsied with the assistance of imaging guidance. This will involve core needle biopsies conducted by a radiologist. Processing of cores will be as follows:

- Core 1) formalin- provided by the institution's pathology department. Sample is processed through surgical pathology. Once all samples are obtained, or at an intermediate timepoint in the study, a request for 20 unstained slides or the tissue block from this specimen will be made.
- Core 2) snap frozen.- handled by institutions path department. Samples should be stored at -80°C or in liquid nitrogen until batch shipment on dry ice.
- Core 3) EM fixative- provided by [name] lab (please email [contact] to request EM fixative).
- A sesame seed size sample of tissue can be fixed in EM fix and stored at 4°C (regular refrigerator) until batch shipment.

Core 4) additional research sample

Timepoints for serial tumor biopsies will be

- 1) baseline
- 2) C1D21 ± 7 days

These timepoints may be changed/modified at the discretion of the prinicipal investigator/study chair since the precise timing of successfully measuring the biological effect of drug intervention is not known.

7.3.2 Measuring autophagy induction and autophagy inhibition in tumor tissue.

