8.0 STUDY CALENDAR

Trial Period:	Treatment 0	Cycl	es (28 d	lays	, stı	ıdy a	asse	essr	nents	End of	Post-Trea	itment	
	planned for	D1	of e	ach	сус	le)				•	Treatment			•
Treatment Cycle/Title:	Screening Visit	1	2	3	4	5	6	7	8	Beyond 8 Cycles ¹² 9+	EOT	Safety Follow- up	Follow Up Visits	Survival Follow-Up
Scheduling Window (Days):	-28 to -1		± 3	± 3	At time of Discontinuation	30 days post EOT ⁷	As per standard of care post discon of treatment ⁵	Every 12 weeks⁵						
Informed Consent	Х													
Inclusion/Exclusion Criteria Assessment	х													
Demographics and Medical History	х													
Prior and Concomitant Medication Review	х	х	x	x	x	x	x	x	x	х	х	х		
Drug distribution		Х	Х	Х	Х	Х	Х	X	Х	X				
Post-study anticancer therapy status											Х	Х	Х	х
Survival Status														Х
Adverse Event Assessment	х	х	х	х	х	х	х	х	х	Х	Х	х		
Full Physical Examination	х	х	х	х	х	х	х	х	х	х	Х	х		
Eye Exam ¹⁴	Х		Х					Х		X4				
EKG	Х	Х	Х	Х	Х	Х	Х	Х	Х	X				
Vital Signs and Weight	Х	Х	Х	Х	Х	Х	Х	Х	Х	X	Х	Х		
ECOG Performance Status	х	х	х	х	х	х	х	х	х	х	Х	Х		
Pregnancy Test – Urine or Serum β-HCG ³	х	х												
PT/INR and aPTT	X ¹¹		1	1	1		1							
CBC with Differential ¹⁰	X ¹¹		Х	Х	Х	Х	Х	Х	Х	Х	Х	Х	Х	

UPCC 21520

Trial Period:	Treatment C planned for	reatment Cycles (28 days, study assessments lanned for D1 of each cycle)							essr	nents	End of Treatment	Post-Treatment		
Treatment Cycle/Title:	Screening Visit									Beyond 8 Cycles ¹²	FOT	Safety Follow-	Follow Up Visits	Survival Follow-Up
	VISIC	1	2	3	4	5	6	7	8	9+	201	up		10100-00
Scheduling Window (Days):	-28 to -1		± 3	± 3	± 3	± 3	± 3	± 3	± 3	± 3	At time of Discontinuation	30 days post EOT ⁷	As per standard of care post discon of treatment ⁵	Every 12 weeks⁵
Comprehensive Serum Chemistry Panel ¹⁰	X ¹¹		Х	х	х	Х	х	х	х	x	Х	х	Х	
Transthoracic Echo	х			X ⁴			X ⁴			X4				
Tumor Imaging ⁶	X ⁸		X9		Х 9		X9		X9	X _ð	х		X ¹³	
Tumor biopsies ¹	Х	Х												
Research Blood Collection ²	Х	х	Х	х	х	х	х	х	х	Х	Х			

1. On-study tumor tissue collection is optional and should be performed prior to treatment and then at C1D21±7 days. Preference will be made to biopsy the same site for both biopsies, if safe and feasible.

2. Up to 60mL of blood will be collected for research studies. Please refer to the Study Laboratory Manual for additional details.

3. Female subjects of reproductive potential only. A negative pregnancy test is required within 72 hours of Cycle 1/Day 1.

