- 12. Treatment will continue indefinitely in the absence of (1), documented disease progression, (2) unacceptable adverse event(s), (3) intercurrent illness that prevents further administration of treatment, (4) investigator's decision to withdraw the subject, (5) subject withdrawal of consent, (6) pregnancy of the subject, (7) noncompliance with trial treatment or procedure requirements, (8) institution of alternative systemic treatment, or (9) other administrative reasons.
- 13. Tumor imaging in post-treatment follow-up will be performed per routine care and at the discretion of the treating investigator.
- 14. See table 3 for required time-points. Suspicion for eye toxicity will prompt an unscheduled research eye exam. To assure the ocular safety of the subjects, at each ocular exam visit the Ophthalmology sub-Investigator will perform a comprehensive eye examination of both eyes. The specified assessments within the ophthalmic examination are reflective of consensus guidelines [American Academy of Ophthalmology Preferred Practice Patterns Committee, 2005] and will be performed according to the Investigator's usual practice in addition to the assessment of visual acuity in the study and will include:

-Ocular alignment and motility, pupillary function, and visual fields by confrontation

-External examination of the eyelids and eyelashes

-Slit-lamp biomicroscopic examination of the anterior segment structures: eyelid margins, conjunctiva, sclera, cornea, anterior chamber, iris, lens, and anterior vitreous

-Intraocular pressure (IOP) measurement

-Following dilation of the pupil, continued slit-lamp biomicroscopic examination of anterior segment structures with clinical grading of lens opacity

-Fundus slit-lamp biomicroscopic examination, including use of accessory diagnostic lenses, to view the vitreous, retina, macula, vasculature, and optic nerve

-if changes on exam or ancillary testing are noted, fundus photography and autofluorescence should be utilized if clinically indicated.

To account for major holidays and unforeseen events such as inclement weather, scheduled visits and testing can occur +/- 1 week, as long as there is documentation as to why they did not occur according to intended schedule. Archival tumor tissue can be obtained at any point during study enrollment and treatment timeline

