11.5 Plans for Data Analysis

Primary

- The objective response rate and 95% exact confidence interval will be calculated.
- All observed toxicities will be graded and tabled (worse grade experienced in all cycles). The
 overall rate of > grade 3 toxicity and 95% exact confidence interval will be calculated.

Secondary

• Progression-free survival and overall survival will be estimated by the method of Kaplan and Meier. Median values and 95% confidence intervals will be calculated.

Exploratory

- Associations between objective response and expression of biomarkers pre-treatment will be tested using nonparametric Wilcoxon rank sum test. Comparisons of pre- and post-treatment biomarker expression will be conducted using Wilcoxon signed ranks test for paired data.
- Describe autophagic vesicles/cell in tumor tissue at various time points using descriptive statistics and scatter plots.
- To evaluate HCQ pharmacokinetics and pharmacodynamics to determine whether changes in blood-based autophagy biomarkers (ctDNA KRAS allelic frequency) reflect tissue-based changes in autophagy (autophagic vesicles/cell), the nonlinear mixed–effects modeling approach (NONMEM) will be used to perform a full population PK analysis. PK-PD analyses to be conducted by University of Sciences of Philadelphia. Analysis methods – See Section 18. The key variables for the population include the Cmax and half life. Population PK will be assessed and qualitatively compared to population PK findings from other HCQ studies. No hypothesis testing will be performed for any of the vairables.

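### Section 11's exploratory text does not match the trial's own sampling and objectives: a Week 6 tissue label with no Week 6 biopsy, ctDNA KRAS in place of the plasma autophagy proteins, methods in a Section 18 that does not exist, and no endpoint for ctDNA change

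*Combined protocol and SAP*

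**What the plan says.** Tissue timing. The objectives in 11.2 include "differences in pre-treatment and Week 6 tumor expression of PPT1, LC3, ALDH1A1 and HLTF biomarkers", and 11.3 repeats the Week 6 label: "PPT1, LC3, ALDH1A1 and HLTF will be measured in pre-treatment tissue and at Week 6". Section 1.3 instead aims "To monitor changes on a repeat biopsy after 3 weeks of treatment with HCQ + B". Sections 7.1 and 7.3.1 give baseline and C1D21 ± 7 days, and footnote 1 of the study calendar (Section 8.0) says "On-study tumor tissue collection is optional and should be performed prior to treatment and then at C1D21±7 days".

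Blood marker. The PK-PD bullet in 11.5 asks whether "changes in blood-based autophagy biomarkers (ctDNA KRAS allelic frequency) reflect tissue-based changes in autophagy (autophagic vesicles/cell"). Sections 1.3, 2.5 and 7.4.1 name IL-8, interleukin-1 beta, LIF, DKK3 and FAM3C as the candidate blood markers, with 1.3 adding other cytokines. Section 7.4.1 plans to set these proteins against electron microscopy. Section 1.3 lists ctDNA KRAS as an objective of its own.

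Methods. Section 11.3 refers HCQ PK-PD to 11.5, and both 11.2 and 11.5 refer to Section 18. The 11.5 bullet ends with "No hypothesis testing will be performed for any of the vairables".

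ctDNA. Change in ctDNA KRAS is a secondary objective in the Study Summary and 11.2, and a correlative objective in 1.3.

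**The concern.** Section 2.5 gives the reason for the correlative work: to test whether HCQ adds to binimetinib by inhibiting autophagy. Section 11 is where an analyst looks for what to measure, when, and how to compare it, and on this question it disagrees with the sections that govern sampling. An analyst who follows 11.5 as printed would relate a tumour-DNA allele fraction to autophagic vesicles and never examine the proteins chosen as autophagy markers. The IHC endpoint would carry a time label that fits no scheduled tissue. An objective called secondary in two places would reach the report with no agreed definition. Biopsies are optional and only about 5 patients are expected to have a pair, so choices left open here would be made after the few data points are in hand.

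**Working it through.** The plan states no figure to reproduce on this point. The check is arithmetic on study days, followed by a comparison of sections. Assumptions: day 1 is C1D1, cycles are 28 days (4.1), and Week 6 means the sixth week of treatment.

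1. **Biopsy window.** 21 − 7 = day 14 and 21 + 7 = day 28, so days 14 to 28.
2. **Week 6.** The first day is 5 × 7 + 1 = 36 and the last is 6 × 7 = 42, so days 36 to 42.
3. **Gap.** Shortest 36 − 28 = 8 days; longest 42 − 14 = 28 days.
4. **With the calendar's allowance.** The closing note of Section 8.0 says "scheduled visits and testing can occur +/- 1 week" for holidays and unforeseen events. Added to the window, the latest biopsy is 28 + 7 = day 35, still before day 36.
5. **Blood marker.** Section 11 names none of the five proteins listed in 1.3. The one marker it names, ctDNA KRAS, is not on the 1.3 list of autophagy markers.
6. **Methods trail.** 11.3 points to 11.5; 11.5 and 11.2 point to Section 18. The contents list and the body both end at 11.7, followed by the references and Appendices A and B. Section 7.2.3 does give population PK methods for HCQ. That model describes HCQ concentrations; it does not say how a blood marker is compared with vesicles/cell. Section 7.2.1 says PK will be correlated with PD, and 7.2.3 says exposure will be used in correlative analyses, but neither gives a method.
7. **PK text.** 11.5 names Cmax and half-life as key variables. 7.2.3 lists CL/F, Vd/F, AUC, Cmax and Cmin, and not half-life. 7.2 assigns PK analysis to one university, and 11.5 assigns PK-PD analysis to another.
8. **ctDNA change, place by place.** Study Summary: secondary. 1.2: absent. 1.3: correlative. 11.2: secondary. 11.3: no line. 11.5, Secondary: PFS and OS only. 11.5, Exploratory: only the parenthesis that labels it an autophagy marker.
9. **Lag if plasma at C2D1 is paired with the biopsy.** Lag = draw day − biopsy day, and C2D1 is nominally day 29. Nominal: 29 − 28 = 1 to 29 − 14 = 15 days. With the ± 3 day visit window: 26 − 28 = −2 to 32 − 14 = 18 days. With ± 1 week on both (biopsy days 7 to 35, draw days 22 to 36): 22 − 35 = −13 to 36 − 7 = 29 days. A delayed cycle start would move the draw later still.

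**The case against.** The best defence is that every operational section agrees on C1D21, so tissue would be taken at the intended time whatever Section 11 calls it, and that 7.3.1 says "These timepoints may be changed/modified at the discretion of the prinicipal investigator/study chair". The first half stands: a reader might infer that biopsies will be mistimed or a Week 6 sample lost, and the documents do not support that. The second half does not remove the conflict. Permission to move a time point neither schedules a Week 6 biopsy nor reconciles two fixed statements.

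On ctDNA, a reader might infer that it has no analysis at all. That goes too far, because 11.5 does name its change as something to compare with vesicles/cell. What is missing is an endpoint definition and a summary of its own. A reader might also infer that no blood is drawn for it. The calendar schedules research blood and refers to a laboratory manual that is not among these documents, so no missing sample can be claimed.

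On tiers, the Study Summary has only primary and secondary headings, so a secondary listing there is weak evidence by itself. The substantive conflict is between 11.2 and 1.3, which both have a correlative tier and place ctDNA differently.

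On methods, it is fair to say that 7.4.1 fixes the comparator, that 11.5 already plans descriptive statistics and scatter plots for vesicles/cell, and that about 5 optional pairs do not justify elaborate modelling. This argues for a short descriptive method. It does not excuse pointing to a section that is not there.

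**Conclusion.** The concern holds as an internal contradiction in Section 11.

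- **Time label.** The Week 6 label lies 8 to 28 days after the scheduled biopsy window, and at least 1 day after it with the calendar's full allowance (36 − 35). This rests on counting from C1D1 and reading Week 6 as days 36 to 42. Reading it as six completed weeks does not bring it inside the window.
- **Blood marker.** The marker named in 11.5 is not among those named in the trial's own objective and rationale, so 11.5 as printed does not answer the 1.3 objective.
- **Methods.** No section says how blood markers will be compared with tissue, or HCQ exposure with PD.
- **ctDNA change.** It has no endpoint, no stand-alone summary and no consistent tier.

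A reader might infer that the trial's main conclusions are at risk. They are not: the two-stage response rule and the safety analysis use none of these data. The point should be corrected before the correlative analyses are run.

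**What to change.** 1. In 11.2 and 11.3, replace Week 6 with the scheduled on-treatment biopsy (C1D21 ± 7 days), or otherwise reconcile these sections with 1.3, 7.1, 7.3.1 and the calendar.
2. In 11.5, replace the ctDNA parenthesis with the plasma proteins of 1.3 and 7.4.1.
3. Replace both Section 18 references with three items:
   - 7.2.3 for population PK.
   - A per-patient plot, without a test, of the change in each protein against the change in vesicles/cell. Use one pre-specified on-treatment draw, such as C2D1, and record the actual lag between biopsy and draw.
   - A descriptive plot of model-derived HCQ exposure against the same changes.

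   This agrees with the bullet's own statement that nothing will be tested.
4. Reconcile 11.5 with 7.2 and 7.2.3 on the key PK variables and on which institution does which analysis. Section 7.2.3 also still refers to a D+T combination and to a phase I portion of the trial, which should be corrected if it becomes the methods reference.
5. Put ctDNA change in one tier across the Study Summary, 1.3 and 11.2. Add an endpoint line in 11.3 (within-patient change from pre-treatment) and a descriptive summary in 11.5, after confirming which samples are allocated to ctDNA.

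The cost is wording in Section 11 and the objective lists, the reconciliation of the PK text, and one check against the laboratory manual. No added visit or sample is proposed. With about 5 pairs and a lag that is nominally 1 to 15 days and wider in practice, the plots remain hypothesis-generating.
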